
On August 2018, the NHS DPP released a new framework for 'Healthier You: NHS Diabetes Prevention Programme'. The aim of the new framework is to expand the programme and to improve take-up and adherence to the DPP, including better targeting of the working age population and addressing delays associated with courses in rural areas.

The new framework also includes implementation of digital support for diabetes prevention alongside existing face-to-face provision, which has the potential to be one of the largest implementations of a digital programme in the NHS. Recruitment onto the new framework will start in August 2019, covering 45% of the sites in England, with the remaining 55% covered in 2020.

For operational reasons the DPP team re-procured the DPP intervention before the digital pilot could report. Therefore, the initial re-procurement focused mainly on face to face prevention programmes. However, all five of the new framework providers have been required to offer a digital prevention programme to people who decline invitation to the face-to-face programme. Once the results from the Digital DPP pilot are released, the DPP management team might decide to open up choice between face-to-face or digital intervention.

Aims and objectives

The overall aim of the DIPLOMA research programme is to provide a comprehensive assessment of the implementation, delivery and outcomes of the NHS DPP to inform commissioning.

The individual work package aims are as follows:

Work package 1 Access and Inequality

To assess whether sociodemographic factors influence access to the NHS DPP, and to explore the experience of patients and professionals in accessing the NHS DPP

Work package 2 Implementation

To assess the process of implementation of the NHS DPP, and explore the barriers and facilitators that affect the implementation of the NHS DPP

Work package 3 Service Delivery and Fidelity

To assess the theory, techniques and content of the NHS DPP, examine variation in delivery, and report the extent to which the NHS DPP is delivered with fidelity

Work package 4 Outcomes

To assess what outcomes participants achieve in the NHS DPP, and whether outcomes vary by services delivered and patient characteristics

Work package 5 Comparative Effectiveness

To assess whether the NHS DPP is more effective than usual care in reducing conversion of non-diabetic hyperglycaemia to diabetes, eventually reducing diabetes prevalence in England

Work package 6 External Validation

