- b) ELSA adults aged 50+ with 457 wave 2 participants, 1,297 wave 4 participants, 1,315 wave 6 and 806 wave 8 participants with HbA1c between 42-47 mmol/mol
- c) NDA (comparative observable factors e.g. age, gender, IMD, comorbidity; flags for non-diabetic hyperglycaemia)

Research question WP 1.2: Are there inequalities in the referral of patients to the NHS DPP?

Once a diagnosis of non-diabetic hyperglycaemia has been made, the GP may or may not refer the patient to NHS DPP. This decision to refer may be influenced by both the GP and patient, and may be related to patient or professional perceptions of the value of the service.

Method: We will compare the observable characteristics of patients referred to the NHS DPP in the Minimum DataSet (MDS) to patients identified with non-diabetic hyperglycaemia in the NDA dataset and those in surveys using analogous methods as those described in WP 1.1. The MDS contains information that providers of the DPP are contractually obliged to collect in order to receive financial reimbursement. It contains dates and sources of referrals and information about subsequent programme attendances, as well as participant outcome measures, as recorded by the providers of the programme.

Research question WP 1.3: Are there inequalities in attendance and completion of the NHS DPP?

Following a positive identification of non-diabetic hyperglycaemia, patient uptake and adherence to the NHS DPP intervention may vary. We can examine this in the MDS, using relevant codes for 'referral to the NHS DPP intervention', 'intervention started', 'declined' and 'completed'.

Method: Using MDS data (observable patient characteristics e.g. age, gender, IMD, co-morbidities). for those referred and on the programme we will compare the characteristics of patients and how this varies with course uptake and completion, the characteristics will be compared to patient characteristics in the NDA and survey datasets to understand at what point the characteristics of patients begins to change.

Research question WP1.4 What is the experience of patients and professionals in accessing the NHS DPP?

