Methods: NHS DPP is designed to increase individual awareness and help them to reduce their risks through lifestyle changes. We will use the ELSA (2004-2014) data to: a) estimate the benefits of lifestyle changes on the diagnosis of diabetes; and b) estimate the effect of diagnosis itself on lifestyle changes. We will use multivariable non-linear regression models to predict the benefit of lifestyle changes (measured by physical activity, BMI, consumption of fruit and vegetables) on the likelihood of developing diabetes for those who are at risk of diabetes in the first observation in ELSA (using glucose level measurements in ELSA). We will estimate these benefits by age and gender.

We will then determine the wider behavioural effects of the NHS DPP that arise from a non-diabetic hyperglycaemia diagnosis. International evidence suggests that individuals improve their lifestyles in response to diagnosis. However, patients with non-diabetic hyperglycaemia could also decide to indulge in less healthy lifestyles anticipating increased and effective treatment in the future. We will estimate this behavioural response using dynamic models of lifestyle choices and comparing diabetics to a statistically defined group of people at 'risk' of developing diabetes using the propensity score model 121 using a similar US survey, the Health and Retirement Survey.

Research questions WP 7.4 - Is the overall NHS DPP cost-effective compared to usual care? How does incorporation of equity consequences affect the overall cost effectiveness of NHS DPP? What changes to the NHS DPP would improve its short and long-term cost effectiveness?

Methods: It is expected that the NHS DPP will increase costs in the short term as participants make greater use of health services to better identify and manage their newly-identified needs. Health-related quality of life may also deteriorate in the short term as participants adjust to the discovery that they are at higher risk. As such, it is likely that the health benefits and cost reductions that are expected from the NHS DPP will be accrued in the longer-term.

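### WP 7.3 targets the behavioural response to a diagnosis of non-diabetic hyperglycaemia, but its planned contrast identifies at best the response to a diabetes diagnosis, and no assumption links the two

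*Protocol*

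**What the plan says.** The Methods under Research questions WP 7.3 have two parts. The first uses ELSA, 2004 to 2014, to "estimate the benefits of lifestyle changes on the diagnosis of diabetes; and b) estimate the effect of diagnosis itself on lifestyle changes". The benefit of lifestyle change is to be estimated by age and gender among people at risk of diabetes when first observed.

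The second part says the team will "determine the wider behavioural effects of the NHS DPP that arise from a non-diabetic hyperglycaemia diagnosis". It notes international evidence that people improve their lifestyle after a diagnosis, then warns that people with NDH could do the reverse because they expect effective treatment later. It continues: "We will estimate this behavioural response using dynamic models of lifestyle choices", and the means is "comparing diabetics to a statistically defined group of people at 'risk' of developing diabetes". The sentence ends by citing a propensity score model and "using a similar US survey, the Health and Retirement Survey".

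Three other places bear on this:

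- Background and Rationale defines NDH as raised glucose that falls short of a diagnosis of type 2 diabetes.
- WP 1.1 describes the survey sample as "ELSA adults aged 50" and over.
- The section on the digital programme says the new framework aims at "better targeting of the working age population".

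**The concern.** The target is what people do differently once told they have NDH. The method observes people told they have diabetes. These are different events in different people, and nothing in the protocol says why one response should stand for the other.

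WP 7.3 asks for the expected long-term benefits and costs of introducing the programme, and the WP 7 overview promises benefits for non-participants as well as participants. This paragraph is where WP 7 sets out to measure the wider effect of being identified. Followed as written, it would report a diabetes-diagnosis response under the name of an NDH-diagnosis response.

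**Working it through.** The protocol gives no effect size, sample size or power for WP 7.3, so there is no figure to reproduce. The check compares the target with the contrast.

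**Step 1: who is in each group.**

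| Element | Target in WP 7.3 | Contrast planned in WP 7.3 |
|---|---|---|
| Diagnosis received | NDH | Diabetes |
| People given it | People with NDH | People with diabetes |
| Comparator | Same kind of people, not told | A statistically defined at-risk group; awareness of NDH not stated |
| Data | Not tied to one source | ELSA in the first part; a US survey named in the last sentence |

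By the Background definition, the first two rows of the contrast column contain nobody from the target column. The people closest to the target sit in the comparator.

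**Step 2: what the contrast estimates if everything else works.** Assume the propensity score balances the groups perfectly and that responses are the same for everyone. On a scale where higher means healthier, let

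- b = lifestyle with no diagnosis,
- d = change caused by a diabetes diagnosis,
- n = change caused by an NDH diagnosis (the target),
- a = share of the at-risk comparator who already know they have NDH.

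Then

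- people with diabetes: b + d
- comparator: b + a·n
- planned contrast: (b + d) − (b + a·n) = d − a·n
- error if reported as n: d − a·n − n = d − (1 + a)·n

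If nobody in the comparator knows (a = 0), the contrast is d and the error is d − n. If all of them know (a = 1), the contrast is d − n, the step from one label to the next, and the error is d − 2n. The error vanishes only when d = (1 + a)·n. A propensity score can balance who the people are; it cannot change which diagnosis they received.

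**Step 3: what the documents give for d, n and a.** No values. On direction, the general evidence cited points to improvement after diagnosis, while the caution about NDH allows n to be negative. If d > 0 and n < 0, the contrast d − a·n is positive while the target is negative. That is a possibility within the protocol's own text, not a finding.

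**Step 4: is there a repair elsewhere?** No bridging assumption appears. The sensitivity analyses under WP 7.4 vary model inputs and structure in general terms and do not mention this transfer.

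**Step 5: ages.** The age limits stated under Work package 9, for self-referral and for screening practice lists, are 18 to 79. ELSA as described starts at 50. Estimating by age and gender cannot yield values for 18 to 49. The protocol gives no age distribution of participants, so the weight of that gap is unknown.

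**The case against.** The strongest objection concerns reach. WP 7.4 names its effectiveness input: conversion to diabetes in the National Diabetes Audit, comparing people who accessed the programme with usual care. Both groups come from patients already identified as at risk, so any response to the label is present on both sides. The other listed inputs are programme costs, diabetes costs and published complication risks. The WP 7.3 behavioural estimate is not among them. A reader might infer that the cost-effectiveness result is distorted; the documents do not support that. What remains is that WP 7.3 is a research question in its own right, and the audit comparison, for the same reason, cannot supply the effect of identification.

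Three other strong readings also fail:

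- **That the estimate certainly comes from US data.** The first part assigns the effect of diagnosis to ELSA, and the closing mention of a US survey may describe the cited propensity model. The source needs clarifying, but ELSA would not cure the mismatch.
- **That the comparator is undiagnosed.** The text says only that it is statistically defined.
- **That the diabetes response is an upper bound on the NDH response.** Nothing in the documents orders the two.

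It may also be said that the caution about less healthy habits expresses uncertainty the analysis is meant to resolve. That is fair as to intent, but a contrast with no identifiable NDH-diagnosis group cannot resolve it.

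On age, working age overlaps 50 and over, and the explicit 18 to 79 limits belong to the self-referral route and the WP 9.3 interview study. The age point is therefore secondary.

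**Conclusion.** The mismatch stands on the wording of a single paragraph. WP 7.3 names the response to an NDH diagnosis as its target, and its contrast identifies at best the response to a diabetes diagnosis. The two agree only under a condition that the protocol does not state and that its own caution about NDH patients puts in doubt.

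The size and sign of any error are unknown. A reader might be tempted to quantify it by applying the 16% risk reduction per kilogram in the Background to assumed weight changes after each diagnosis. The protocol gives no such weight changes, so the result would reflect only the values chosen. A reversed sign is likewise possible but not shown.

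The consequence is confined to what WP 7.3 can claim. This rests on two readings: that the words introducing the estimate refer back to the NDH response, which is the natural sense, and that the WP 7.4 input list is complete as far as effectiveness is concerned.

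**What to change.** Change the WP 7.3 Methods as follows:

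1. Do not report this contrast as the response to an NDH diagnosis. Label it as the response to a diabetes diagnosis.
2. State the transfer from diabetes to NDH as an explicit assumption. Use the estimate only as a scenario, not as a bound, and vary its size and sign, including zero and adverse responses.
3. Say which survey supplies the data for the effect of diagnosis, and whether members of the at-risk group may already know they have NDH.
4. Label the ELSA lifestyle-benefit estimates as applying to ages 50 and over, and vary the values for younger adults in sensitivity analysis.

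These steps cost some wording and a few extra scenario runs.

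As an optional supporting analysis, compare BMI change in CPRD between people just above and just below an HbA1c of 42 mmol/mol, the lower limit of NDH used in the protocol. CPRD access is approved, and HbA1c and BMI are already planned variables in WP 5. The period before the programme began is preferable, because afterwards an NDH code can lead to referral and the effect of the label would mix with that of the programme. A simple comparison of coded and uncoded patients is weaker, since WP 5.1 itself allows that coded cases may be more severe. There are two costs. CPRD holds little on diet or activity, so most of the lifestyle measures planned in WP 7.3 would be lost. How often crossing 42 mmol/mol led to a recorded diagnosis would also have to be checked first.

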These two anonymised datasets are supplied to us by NHS England, collected from patients participating in the NHS DPP (individual characteristics, referral source, extent of participation in the DPP, and health outcomes). No personal details will be available to the research team. We already have the first dataset (face-to-face MDS, as used in the previous WP4 analysis) and NHSE have agreed to provide us with the second dataset (digital DPP). The second dataset contains similar variables, but on a different population. We are signing a Memorandum of Understanding with NHSE to cover the data sharing and we will follow the same UoM information governance procedures as our current DIPLOMA analyses.

Power calculation

HbA1c at 6 months among those taking the F2F DPP is 39.9 mmol/ml (SD 4.08). A reduction in HbA1c of 5 mmol/ml (0.5%) or more is considered to be clinically important so if the difference in the means of the two groups is less than 5 they can be regarded as having a similar effect. Assuming a standard deviation in both F2F and digital DPP of 4.08, 90% power, alpha 5% and 5-to-1 allocation of controls to cases, to observe a difference of 2 mmol/ml we would need a total of 486 people (81 digital, 405 F2F). There are 2200 digital participants with 6 month outcomes, which should provide sufficient numbers, after matching.

Missing data

Multiple imputation by fully conditional specification will be used to reduce bias due to missingness (up to 30% among covariate values in the F2F MDS).24, 25 Multiple imputation has already been applied to the F2F dataset, and a similar approach will be implemented in the digital dataset.

The analysis of clinical effectiveness will focus on completers: in both datasets, outcome data was only collected on those who stayed in the programme until the outcomes were recorded, so there will be considerable, systematic bias in terms of differences between responders and non-responders.

Analysis

1. Descriptive statistics

We will describe patient participation (registrations, starts and completion) in digital and face to face, and explore differences between digital and face to face patients.

2. Differences in participation (start and completion)

We will estimate differences in participation (registration, start and completion) between digital and face to face. Differences will be explored using three approaches

- a) Raw (uncorrected) differences in participation.

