- (b) NHS DPP attenders.

In practices where DPP attendance is not recorded we will send questionnaires to referred patients and ask about NDPP attendance as part of the questionnaire, to place each individual responder in the relevant attenders or non-attenders group. On average, 50% of people referred to DPP attend the programme, so this approach should result in roughly equal groups. Additionally, in practices which hold clinics to review patients at risk of diabetes, study information can be provided to eligible patients.

A high recruitment rate is essential to minimise bias in the validation sample. The questionnaire will be as short as practicable. We will use intensive recruitment and collection methods, working closely with professionals and the NIHR CRN locally, piloting the questionnaire prior to use with patients, and using financial incentives to patients and practitioners, ¹¹⁶¹¹⁷ aiming for a 70%-80% recruitment rate.

The high response rate required means that this work-package is 'high-risk'. If we manage to reach this target then our findings in this section will augment the quality of the analyses in work-package 5 and 7. However, the analyses in those work packages are not dependent on the success or otherwise of this survey. If a lower response rate is evident, the data will still be of considerable value, as it will allow us to examine the role of psychological and social factors in access inequalities, and study the relative influence of GPs and patient self-selection on NDPP participation.

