Analysis: Descriptive statistics will be used to characterise the groups of people who attend, and do not attend, the DPP across a range of demographic, attitudinal and psychological factors; and comparisons will be made to available national data (e.g. from the DPP "minimum dataset"). We will use univariate and multivariate logistic regression methods to estimate and compare the role of the various factors in influencing attendance at the NHS DPP intervention. We will also compute a propensity score for each individual representing their probability of attending given their particular combination of factors, to provide a picture of the extent to which these factors as a whole are associated with attendance. The individual factor and propensity scores will further be used in combination with analyses of CPRD, the minimum dataset, and other data sources to assess the extent to which any observed associations between DPP referral and attendance and subsequent development of diabetes are confounded with demographic differences and to adjust the associations for those differences. These results will further feed into the health economics analysis of the cost-effectiveness of the programme, particularly in relationship to estimating effectiveness in patient sub-populations.

Work package 7 - Comparative Long-term Cost Effectiveness ([name] and [name])

Aims: To assess whether the NHS DPP is cost-effective compared to usual care in terms of long-term costs and benefits

Rationale: As with work package 5, commissioning of the NHS DPP will also be dependent on a rigorous demonstration of cost-effectiveness. Diabetes is associated with compromised quality and length of life and significant long-term health care utilisation. Effective prevention has the potential to generate health benefits and significant cost-savings over the longer term. This work package will utilise economic modelling to explore the longer term costs and benefits of the NHS DPP.

Overview of methods: This work package will estimate the overall cost effectiveness of the NHS DPP taking account of the costs incurred by commissioners to deliver the programme and the long-term health benefits for participants and non-participants. It will draw together the findings of the other work packages and use an economic model to summarise the overall cost-effectiveness of the programme as implemented and identify major opportunities for enhancing its cost effectiveness.

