Research questions WP 7.1 - What are the additional costs of implementing and providing NHS DPP to the range of commissioning agencies involved?

Methods: We will estimate the additional costs of implementing and providing NHS DPP using information from the national commissioning agencies and the Implementation work package (WP2). These costs will include the contracted amounts paid to the NHS DPP providers and the costs to general practices of identifying, referring and following-up on 'NHS DPP eligible' patients. We will need to identify the additional costs incurred by general practices due to the introduction of the NHS DPP, excluding the costs that they would incur anyway in identifying and managing this patient group. We will also examine whether general practices transfer the costs of providing services to the target group as a result of the introduction of a targeted scheme for these patients paid for by other means.

Research questions WP 7.2 - What are the short-term health benefits of NHS DPP to participants in the scheme, and what are the cost consequences of the short-term changes in health service utilisation for participants in the NHS DPP?

Methods: We will use data from the Outcomes work package (WP4) to estimate the average increases in health-related quality of life reported by NHS DPP participants. We will model the expected effects on quality of life using mapping to the EQ5D 5L. We will use data from participants on health service utilisation and figures from NHS Reference Costs and the Unit Costs of Health and Social Care to estimate the changes in costs. We will focus initially on the short-term effects reported by participants.

Research questions WP 7.3 - What are the expected long-term health benefit consequences of the introduction of NHS DPP? What are the expected long-term cost consequences of the NHS DPP?

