Decision-analytic models are frequently used within economic evaluations, to extrapolate beyond observed data and to estimate the long-term effects of an intervention. Often, this involves modelling a hypothetical cohort over a lifetime horizon, using multiple sources of data. Inputs into decision-analytic models include parameters such as the probabilities of different events occurring (referred to as transition probabilities), the costs associated with events or resource use, and utility scores, which can be used to estimate quality-adjusted life years (QALYs).

Several decision-analytic models exist in the published literature*, which evaluate the cost-effectiveness of prevention strategies of developing Type 2 Diabetes. These models will be assessed to determine their strengths, weaknesses, validity and usability. In light of these assessments, one of the existing models will be selected and adapted, so that it can be used to evaluate the cost-effectiveness of the NHS DPP. As there is no model that currently evaluates the effectiveness of the NHS DPP, we will require effectiveness data to inform the model parameters.

The National Diabetes Audit (NDA) contains information on all of the patients identified as being at risk of developing Type 2 Diabetes, as well as the number of these that go on to develop the condition. This data will be used as an input in the decision-analytic model, comparing the number developing diabetes who have accessed the NHS DPP to those who receive usual care. Access to the data will conditional on an application to NHS Digital, which will be reviewed by an Independent Group Advising on the Release of Data (IGARD), who determine whether the application is ethically acceptable, and that the appropriate data governance structures are in place.

Other data sources will include, the costs associated with implementing and running the NHS DPP, costs associated with the condition of Type 2 Diabetes, and published clinical data on the risk of various comorbidities and complications which arise as a result of Type 2 Diabetes.

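### WP 7.4 feeds the economic model with an undefined 'accessed' versus usual-care contrast, and WP 7.2 with gains among those still reporting, while WP 7.1 costs follow eligible and referred patients; the result can be biased, plausibly in the programme's favour

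*Protocol*

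**What the plan says.** All references are to the Protocol.

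- **Scope (Work package 7, Overview of methods).** The evaluation is to be made "taking account of the costs incurred by commissioners to deliver the programme and the long-term health benefits for participants and non-participants", drawing on the other work packages.
- **Costs (WP 7.1).** "These costs will include the contracted amounts paid to the NHS DPP providers and the costs to general practices of identifying, referring and following-up" patients eligible for the programme. The basis of provider payment (referral, start or completion) is not stated.
- **Short-term benefit (WP 7.2).** WP4 data will be used to "estimate the average increases in health-related quality of life reported by NHS DPP participants". WP4 has no comparator group. The missing-data paragraph of WP 4.5 says of both the face-to-face and the digital dataset that "outcome data was only collected on those who stayed in the programme until the outcomes were recorded", and expects responders to differ systematically from non-responders.
- **Diabetes input to the model (WP 7.4).** The National Diabetes Audit supplies it, "comparing the number developing diabetes who have accessed the NHS DPP to those who receive usual care". No matching or adjustment is stated there.
- **Uptake (Work package 6, Step 2).** "On average, 50% of people referred to DPP attend the programme".
- **What else is planned.** WP 5.2 design 2 compares referred patients with matched patients who were not referred, and its power statement is framed as intention to treat. WP 5.2 design 1 also sets referred patients against matched pre-programme controls.

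**The concern.** WP 7.4 answers the commissioning question, so its effectiveness input matters most. As written, that input is a contrast by uptake. The WP6 rationale describes the WP5 and WP7 comparisons as between people who do and do not participate, and accepts that unmeasured confounding cannot be excluded. Step 1 of WP6 expects health status, motivation and health literacy to influence access, and these may also affect diabetes risk.

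'Accessed' is not tied to any of the groups that WP1 names (eligible, attender, non-attender, completer). With about half of referred people not attending, the arm in which they are counted can change the estimate a good deal, and it is not stated.

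The inputs also follow different groups: eligible and referred people for practice costs, accessers for diabetes, and people still reporting for quality of life. If a mean from a narrower group is carried over to a wider one, the benefit is overstated.

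**Working it through.** WP7 states no effect size, cost or cost-effectiveness ratio, so there is no figure of its own to reproduce. The check is of direction and possible size.

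**Inputs from the Protocol.** Two-year conversion 7.5% and risk reduction 25% (WP 5.2, Sample size, used here only as illustration); attendance among those referred 50% (WP6, Step 2); digital pilot registrations 4,409, of whom 2,687 gave outcome data (WP 4.5, Populations).

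**Assumptions, not in the Protocol.** s is the fraction by which attenders' untreated risk lies below the average referred person's, taken as 5%, 10% or 20%. h is the gain of non-reporters relative to reporters, taken as 0, 0.5 or 1.

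**1. Does the mismatch alone favour the programme?** Per 1,000 referred, with a 25% reduction in attenders and none in non-attenders:

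- True cases avoided: 1,000 × 0.5 × 0.075 × 0.25 = 9.375.
- Benefit summed over accessers only, set against all referral costs: also 9.375. This is neutral, and conservative if non-starters gain anything.
- Accessers' mean benefit applied to everyone referred: 1,000 × 0.075 × 0.25 = 18.75, a 2-fold overstatement.

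So a further step is needed before the mismatch favours the programme.

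**2. Selection into access.**

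- Comparator at average risk: apparent reduction = 1 − (1 − s)(1 − 0.25).
- Comparator made up of non-attenders: at 50% attendance their risk is 0.075(1 + s), so apparent reduction = 1 − 0.75(1 − s)/(1 + s).

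| s (assumed) | Average-risk comparator | Non-attenders as usual care |
|---|---|---|
| 5% | 28.75% | 32.1% |
| 10% | 32.5% | 38.6% |
| 20% | 40% | 50% |

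The true reduction is 25% in every row. The gap between the columns shows why it matters where non-starters are counted.

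**3. Quality of life among reporters.** Reporting share f = 2,687/4,409 = 0.609. If the reporters' mean is applied to all registrants, the overstatement is 1/(f + (1 − f)h):

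- h = 0: 1.64-fold
- h = 0.5: 1.24-fold
- h = 1: 1.00-fold

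**The case against.** The strongest reply is that WP 7.4 merely names a data source. The National Diabetes Audit is also the intended primary source for WP5, WP7 is said to draw on the other work packages, and WP6 results are to feed the economic analysis. 'Accessed' may not mean attended, since WP1 treats access as a process running from identification to completion. WP 7.2 asks about benefits to participants, so reporting participants' change answers its own question, and nothing says that this mean is multiplied over a wider cohort. WP 7.4 itself expects that quality of life may worsen at first. The model has yet to be chosen, and sensitivity analyses on inputs and structure are promised.

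Much of this stands. No passage commits the team to the extrapolating step, so bias is possible rather than established. The pilot's 61% reporting share includes people enrolled for obesity and is not specific to quality of life.

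Three things remain. WP 7.4 states the contrast and does not link it to the WP 5.2 estimate. WP6 says that the WP5 and WP7 analyses do not depend on its survey, which samples only referred people and so cannot address selection into referral. The promised sensitivity analyses do not name uptake.

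A reader might infer that charging costs for everyone while counting benefits only from accessers or completers flatters the programme by itself. Step 1 shows that it does not. The word 'only' would also be wrong: the WP7 overview includes non-participants, and WP 7.3 models benefits from population surveys.

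**Conclusion.** The point holds as a risk of bias. The WP 7.4 input is an undefined, by-uptake contrast with no stated matching. The WP 7.2 input is an uncontrolled change which, by inference from WP 4.5, rests on those who stayed. Neither matches the cost base of WP 7.1 or the scope in the WP7 overview.

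Bias in the programme's favour needs one of two conditions:

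- **Selection.** Lower-risk or more motivated people take up the programme. A true 25% reduction then appears as about 29% to 50% for an assumed 5% to 20% lower untreated risk.
- **Extrapolation.** A mean from accessers or reporters is applied to all referred or registered people: up to 2-fold at 50% attendance, and 1.0- to 1.64-fold for quality of life, depending on what non-reporters gain.

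Both are realistic, because the model runs average inputs through a notional cohort and the Protocol itself expects personal factors to influence uptake. Neither is shown to occur. This is a worthwhile and inexpensive correction, not a demonstrated error in the result.

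**What to change.** **WP 7.4.**

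- Make the matched, referral-based effect from WP 5.2 the base-case input.
- Keep referred non-attenders in the programme arm and model attendance explicitly. The referral-based effect already averages over non-attendance, so it must not be multiplied by attendance again; attendance then drives delivery costs and uptake scenarios.
- Define 'accessed' and use that contrast as a scenario only.
- Sum costs and effects over the same referred cohort, consistent with the inclusion of non-participants in the WP7 overview.

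Referral is itself selected, as WP 5.2 acknowledges, so its planned checks for unmeasured confounding should carry through to the model.

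**WP 7.2.** Do not apply the reporters' mean to starters or referred people without handling attrition. Use imputation, with zero change for non-reporters as a bounding scenario. Zero change as the base case would be a debatable choice, because it fixes the missing values and understates uncertainty.

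**Cost.** Wording and model inputs change, with a little more modelling; the data are already planned. The stated cost-effectiveness figure may be less favourable.
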